13.2.9. Immunogenicity Analyses

The presence of ADA and the presence of NAb will be summarized by disease, cohort, and time.

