10. SUBJECT DISPOSITION

The number of subjects treated, completing the protocol specified duration of study drug, discontinuing study drug early, completing the study, and early withdrawal from the study will be summarized by disease group. The reason(s) for early discontinuation of study drug and early withdrawal from the study will be summarized. The number of subjects in Cohort 1 and Cohort 2 who rollover to Cohort 3 will be summarized. A list of subjects failing any eligibility criteria will be provided.

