13. SAFETY AND TOLERABILITY

13.1. Overall Summary of Safety

An overall summary of treatment-emergent adverse events, which is defined as the AEs occurring or worsening after the start of study treatment, will be provided by disease group, cohort and treatment. All AEs will be coded by MedDRA. The following items will be included in the overall summary:

- Subject incidence of treatment-emergent AEs
- Subject incidence of treatment-related AEs (defined as probable or possible related to study drug)
- Subject incidence of treatment-emergent AEs by maximum CTCAE grade
- Subject incidence of treatment-emergent serious AEs (SAEs)
- Subject incidence of treatment-emergent AEs leading to discontinuation of study drug
- Subject incidence of treatment-emergent AEs leading to discontinuation of study
- Subject incidence of treatment-emergent fatal AEs
- Total number of unique treatment-emergent AE MedDRA preferred terms
- Median number of unique treatment-emergent AE MedDRA preferred terms per subject
- Total number of unique treatment-emergent SAE MedDRA preferred terms
- Median number of unique treatment-emergent SAE MedDRA preferred terms per subject

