13.2. Adverse Event Preferred Term and Body/Organ System Summary Tables

Subject incidence of the following AEs will be provided by disease group, cohort and treatment:

- pre-treatment AEs by MedDRA SOC and preferred term (pre-treatment AEs are those AEs that occurred prior to the start of study treatment)

- treatment-emergent AEs by MedDRA SOC, and preferred term
- treatment-emergent AEs by MedDRA preferred term
- treatment-related AEs by MedDRA SOC, and preferred term
- treatment-emergent AEs by MedDRA preferred term, and maximum CTCAE grade
- AEs leading to study drug discontinuation by MedDRA SOC, and preferred term
- AEs leading to study discontinuation by MedDRA SOC, and preferred term
- treatment-emergent SAEs by MedDRA SOC, and preferred term
- treatment-related SAEs by MedDRA SOC, and preferred term
- AEs leading to death by MedDRA SOC, and preferred term

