13.3. Study Treatment Adherence and Extent of Exposure

Because all dosing will be under direct supervision of study personnel, treatment adherence will not be analyzed. Dosing information will be listed.

The total dose volume (mL) received, the total intended dose volume (mL) and the number of doses received will be summarized for scheduled visits and unscheduled visits by disease group, cohort and treatment. Intended dose volume at each dose administration for Cohort 1 and Cohort 2 is calculated as

$$4 \text{ mg/kg} \times \text{Weight (kg)} \div \text{Drug concentration.}$$

If the weight is greater than 100 kg, the intended dose volume will be calculated using 100 kg. This study uses two drug concentrations, 100 mg/mL and 185 mg/mL.

In addition, relative dose intensity (%), defined as the total dose volume received as a percentage of the total intended dose volume will be summarized for scheduled visits and unscheduled visits by disease group. Listing of dosing information will also be provided.

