17. IMMUNOGENICITY ANALYSES

The presence of ADA will be summarized by disease, cohort and time. The presence of Nab will be summarized by disease, cohort and time.

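### Relative dose intensity, all-cause disposition and ADA/NAb are tabulated without treatment arm, so these three supporting safety outputs pool OMS721 and vehicle in IgAN subjects

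*SAP*

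**What the plan says.** - **Exposure, SAP 13.3.** Received dose volume, intended dose volume and the "number of doses received will be summarized for scheduled visits and unscheduled visits by disease group, cohort and treatment". Relative dose intensity is then defined as the received volume as a percentage of the intended volume, but the "total intended dose volume will be summarized for scheduled visits and unscheduled visits by disease group", with neither cohort nor treatment named.
- **Disposition, SAP 10.** Numbers treated, completing study drug, stopping it early, completing the study and "early withdrawal from the study will be summarized by disease group". The next sentence gives no grouping at all: "The reason(s) for early discontinuation of study drug and early withdrawal from the study will be summarized". Protocol 13.2.2 tabulates disposition by disease and cohort.
- **Immunogenicity.** SAP 17: "The presence of ADA will be summarized by disease, cohort and time", with the same rule for NAb. Protocol 13.2.9: "The presence of ADA and the presence of NAb will be summarized by disease, cohort, and time". Neither names treatment.
- **Adverse events.** The overall summary in SAP 13.1, split by disease group, cohort and treatment, includes "Subject incidence of treatment-emergent AEs leading to discontinuation of study drug". SAP 13.2 introduces its tables, one of which covers AEs leading to study drug discontinuation, with "Subject incidence of the following AEs will be provided by disease group, cohort and treatment".
- **Design.** Cohorts 2 and 3 enrol IgAN subjects only and are randomised 1:1 to OMS721 or vehicle for the first 12 weeks (Protocol 9.1.2). Cohort 1 is open-label, single-arm and mixed in disease.

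**The concern.** Safety and tolerability are the primary objective, and Cohorts 2 and 3 provide concurrent vehicle controls. How much of the intended dose each subject received, and how many stopped drug for any reason, bear directly on tolerability. ADA frequency among treated subjects is the main immunogenicity result.

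Under the stated grouping, the IgAN row for dose intensity and disposition combines Cohort 1 open-label 4 mg/kg, Cohort 2 at 4 mg/kg, Cohort 3 at 370 mg, and vehicle from Cohorts 2 and 3. The ADA row for Cohort 2 or 3 combines drug-treated subjects with subjects who, at that stage, have received only vehicle. A reader of those tables could not make the between-arm comparison that the randomisation provides.

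**Working it through.** **Inputs.** Planned sizes are 16, 10 and 18 for Cohorts 1, 2 and 3 (SAP 4), and 16 + 10 + 18 = 44, the stated total. Allocation in Cohorts 2 and 3 is 1:1 (Protocol 9.1.2). The number of IgAN subjects in Cohort 1, called *k*, is not given, so it runs from 0 to 16. An even split is assumed, and rollover and replacement are ignored.

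**1. Which outputs lose the arm**

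| Output | Grouping stated | Arm visible? |
|---|---|---|
| Doses, received and intended volume (SAP 13.3) | disease, cohort, treatment | yes |
| AEs leading to drug discontinuation (SAP 13.1, 13.2) | disease, cohort, treatment | yes |
| Relative dose intensity (SAP 13.3) | disease | no |
| All-cause completion, discontinuation, withdrawal (SAP 10) | disease | no |
| Reasons for stopping (SAP 10) | none stated | no |
| ADA, NAb (SAP 17) | disease, cohort, time | no |

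The SAP splits the pharmacodynamic summary by treatment (SAP 15), although Protocol 13.2.7 names only disease, cohort and time. It did not do the same for ADA. SAP 21.1 lists one change from the protocol, the duration-of-response definition, so the coarser disposition grouping is undeclared.

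**2. Vehicle share of the IgAN row**

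Vehicle subjects: (10 + 18)/2 = 14. Share = 14/(28 + *k*).

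- *k* = 0: 14/28 = 50%
- *k* = 4: 14/32 = 44%
- *k* = 8: 14/36 = 39%
- *k* = 16: 14/44 = 32%

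**3. Relative dose intensity (assumed means: 80% on OMS721, 100% on vehicle)**

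Pooled mean = [(14 + *k*) × 80 + 14 × 100]/(28 + *k*).

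- *k* = 0: 2520/28 = 90%
- *k* = 4: 2840/32 = 89%
- *k* = 16: 3800/44 = 86%

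A 20-point difference between arms would appear as one figure of 86% to 90%.

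**4. All-cause discontinuation (assumed 3 on OMS721, 0 on vehicle)**

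3/14 = 21.4% against 0/14 becomes 3/28 = 10.7% among randomised IgAN subjects. Any Cohort 1 IgAN subjects enter the same row, and Protocol 8.3.1 gives Cohort 1 a stopping reason of its own.

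**5. ADA before open-label treatment**

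If ADA occurs only on OMS721 at rate *p*, a 1:1 cohort shows *p*/2. Assumed rates of 10%, 20% and 40% would appear as 5%, 10% and 20%. In Cohort 3, with 9 subjects per arm, an assumed 3/9 (33%) would appear as 3/18 (17%).

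**The case against.** A reader might infer that the plan cannot show whether OMS721 subjects miss or stop doses more often than vehicle subjects, or cannot separate the two OMS721 regimens. The documents do not support either reading. Number of doses, received volume and intended volume are reported by arm, AE-related discontinuation is reported by arm twice, and dosing is listed. The AE, laboratory, vital-sign and ECG tables separate 4 mg/kg in Cohort 2 from 370 mg in Cohort 3, and ADA is already split by cohort and time.

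Some things are still not recovered. Arm-level volumes give a ratio of totals or means, not the mean, median, SD and range of per-subject intensity. Raw volumes also vary with weight and with two drug concentrations (100 and 185 mg/mL). AE tables need not capture stopping by subject choice, noncompliance or physician decision, all of which Protocol 8.3.1 allows.

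SAP 12.4 says that all analyses are by disease group, cohort and treatment, which could be read as covering everything. It is the subgroup paragraph of the efficacy section, while SAP 10, 13.3 and 17 state their own groupings. If it were read as global, the SAP would contradict itself and the same edits would be needed. Table shells are kept separately (SAP 20.1) and may already carry a treatment column, which cannot be checked here.

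Two further objections stand. The study is descriptive and not powered for comparisons, with about 5 against 5 and 9 against 9 subjects. A plain split of ADA by randomised arm would also be wrong later on, because Cohort 3 vehicle subjects may receive open-label OMS721 after week 18 and ADA sampling continues through re-treatment and extended follow-up.

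**Conclusion.** The point holds in a limited form. As written, three supporting outputs pool OMS721 and vehicle for IgAN. What is lost is the per-subject dose-intensity distribution by arm, all-cause discontinuation with reasons by arm, and an undiluted ADA/NAb rate.

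Vehicle subjects are about 14 of 28 in Cohorts 2 and 3 and 32% to 50% of the IgAN row. ADA dilution is about one half within Cohorts 2 and 3, and only for samples taken before open-label OMS721. These sizes rest on planned enrolment, an even split and, for ADA, no positives on vehicle. The dose-intensity, discontinuation and ADA rates are illustrations, not expectations.

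Lupus nephritis, membranous nephropathy and C3 glomerulopathy are unaffected, since they occur only in single-arm Cohort 1. The main AE, laboratory, vital-sign and ECG summaries are also unaffected. The disposition grouping additionally departs from Protocol 13.2.2 without being declared. Severity is minor.

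**What to change.** 1. **SAP 10.** Summarise completion, early drug discontinuation, withdrawal and the reasons for each by disease group, cohort and treatment. This also restores the cohort level required by Protocol 13.2.2.
2. **SAP 13.3.** Give the relative dose intensity sentence the same disease group, cohort and treatment grouping as the dose and volume summaries before it.
3. **SAP 17 and Protocol 13.2.9.** Add treatment for ADA and NAb over the initial treatment and 6-week follow-up period. For Cohort 3, show samples taken after the start of open-label re-treatment separately as OMS721-exposed, not under vehicle. Handle Cohort 2 vehicle subjects who roll over to open-label OMS721 in the same way from the point of rollover; Protocol 13.2.1 already makes rollover subjects their own cohort.
4. Check that the separate table shells match.

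The cost is a few lines of SAP text, one phrase in the protocol and extra table columns. No new data, visits or samples are needed.

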13.4. Concomitant and Other Medications

Subject incidence of concomitant medications will be provided by WHODrug preferred term, disease group, cohort and treatment.

13.5. Routine Laboratory Data

Summary statistics for actual values and for change from baseline will be tabulated as appropriate for laboratory results by scheduled visit, disease group, cohort and treatment. Subjects with laboratory values outside of the normal reference range at any post-baseline safety assessment will be listed by disease group, cohort and treatment.

Shifts from baseline laboratory values (normal/abnormal) will be tabulated by disease group, cohort and treatment.

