6. For subjects in Cohort 1, have been on ≥ 10 mg of prednisone or equivalent dose for at least 12 weeks prior to Screening Visit 1.
7. If on immunosuppressive treatment (e.g., cyclophosphamide, mycophenolate mofetil), have been on a stable dose for at least 2 months prior to Screening Visit 1 with no expected change in the dose for the study duration.
8. Have an eGFR ≥ 30 mL/min/1.73 m² calculated by the MDRD equation.
9. Are on physician-directed, stable, optimized treatment with angiotensin converting enzyme inhibitors (ACEI) and/or angiotensin receptor blockers (ARB) and have a systolic blood pressure of < 150 mmHg and a diastolic blood pressure of < 90 mmHg at rest.
10. If female, are either a) not of childbearing potential (i.e., surgically sterilized or postmenopausal for > 1 year), b) have a negative pregnancy test and if sexually active must agree to use two medically reliable forms of contraception throughout the study, or c) have a medically sterilized male partner. Acceptable methods of contraception include a reliable intrauterine device, hormonal contraception, or a barrier method.
11. If male, are either a) not of reproductive potential or b) if sexually active must agree to use a medically reliable form of contraception throughout the study. Acceptable methods of birth control include spermicide in combination with a barrier method, or subject's female partner is willing to use medically acceptable methods of birth control (intrauterine device, hormonal contraception, or a barrier method).

CONFIDENTIAL

No use, disclosure or reproduction outside of Omeros without prior written authorization

Exclusion Criteria:

1. Have a known hypersensitivity to any constituent of the investigational product.
2. Have a hemoglobin < 9.0 g/dL.
3. Have a platelet count < 100,000/mm³.
4. Have an absolute neutrophil count < 500 cells/mm³.
5. Have an alanine transaminase (ALT) or aspartate transaminase (AST) > 5.0 x the upper limit of normal.
6. Have systemic manifestations of Henoch-Schonlein purpura (e.g., joint pain, gastrointestinal bleeding, abdominal pain) within 2 years prior to Screening Visit 1.
7. Have used belimumab, eculizumab, or rituximab within 6 months of Screening Visit 1.
8. Have a history of renal transplant.
9. Have a diagnosis of human immunodeficiency virus (HIV), hepatitis B, or hepatitis C infection, or positive serology at Screening Visit 1 for HIV, hepatitis B, or hepatitis C.

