8. SELECTION AND WITHDRAWAL OF SUBJECTS

8.1. Subject Inclusion Criteria

Subjects may be included in the study only if they meet all of the following criteria:

1. Competent to provide informed consent.
2. Voluntarily provide informed consent in accordance with regulations and governing institutional review board (IRB) or independent ethics committee (IEC) requirements prior to any procedures or evaluations performed specifically for the sole purpose of the study.
3. Are age ≥ 18 years at Screening Visit 1.
4. Have a diagnosis of one of the following:
 - IgAN diagnosed on kidney biopsy
 - Lupus nephritis diagnosed on kidney biopsy (Cohort 1 only)

CONFIDENTIAL

No use, disclosure or reproduction outside of Omeros without prior written authorization

- Primary MN diagnosed on kidney biopsy (Cohort 1 only)
 - C3 glomerulopathy including dense deposit disease diagnosed on kidney biopsy (Cohort 1 only)
5. Have 24-hour urine protein > 1000 mg/24 hours.
 6. For subjects in Cohort 1, have been on ≥ 10 mg of prednisone or equivalent dose for at least 12 weeks prior to Screening Visit 1.
 7. If on immunosuppressive treatment (e.g., cyclophosphamide, mycophenolate mofetil), have been on a stable dose for at least 2 months prior to Screening Visit 1 with no expected change in the dose for the study duration.
 8. Have an eGFR ≥ 30 mL/min/1.73 m² calculated by the MDRD equation.
 9. Are on physician-directed, stable, optimized treatment with ACEIs and/or ARBs and have a systolic blood pressure of < 150 mmHg and a diastolic blood pressure of < 90 mmHg at rest.
 10. If female, are either a) not of childbearing potential (i.e., surgically sterilized or postmenopausal for > 1 year), b) have a negative pregnancy test and if sexually active must agree to use two medically reliable forms of contraception throughout the study, or c) have a medically sterilized male partner. Acceptable methods of contraception include a reliable intrauterine device, hormonal contraception, or a barrier method.
 11. If male, are either a) not of reproductive potential or b) if sexually active must agree to use a medically reliable form of contraception throughout the study. Acceptable methods of birth control include spermicide in combination with a barrier method, or subject's female partner is willing to use medically acceptable methods of birth control (intrauterine device, hormonal contraception, or a barrier method).

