8.2. Subject Exclusion Criteria

Subjects will be excluded from the study for any of the following reasons:

1. Have a known hypersensitivity to any constituent of the investigational product.
2. Have a hemoglobin < 9.0 g/dL.
3. Have a platelet count < 100,000/mm³.
4. Have an absolute neutrophil count < 500 cells/mm³.
5. Have an ALT or AST > 3.0 x the upper limit of normal.
6. Have systemic manifestations of Henoch-Schonlein purpura (e.g., joint pain, gastrointestinal bleeding, abdominal pain) within 2 years prior to Screening Visit 1.
7. Have used belimumab, eculizumab, or rituximab within 6 months of Screening Visit 1.
8. Have a history of renal transplant.
9. Have a diagnosis of human immunodeficiency virus (HIV), hepatitis B, or hepatitis C infection or positive serology at Screening Visit 1 for HIV, hepatitis B, or hepatitis C.

CONFIDENTIAL

No use, disclosure or reproduction outside of Omeros without prior written authorization

10. Have any significant infection requiring antibiotic treatment at Screening Visit 1.
11. Have a malignancy except for adequately treated and cured basal or squamous cell skin cancer, curatively treated *in situ* disease, or other cancer from which the patient has been disease-free for ≥ 5 years.
12. Have an expectation of survival of less than 24 months.
13. If female, are pregnant or breastfeeding.
14. Have received any other investigational drug or device or experimental procedures within 30 days of Screening Visit 1.
15. Are an employee of Omeros, the investigative site, a study staff member, or their immediate family member.
16. Have any condition that the Investigator believes would put the subject at risk from participation.
17. For subjects in Cohort 2 and Cohort 3, have received corticosteroids within the 3 months prior to screening. Subjects in Cohort 1 rolling into Cohort 3 must have IgAN and must have discontinued corticosteroids prior to entry into Cohort 3, but the discontinuation may occur at any time prior to Cohort 3 entry.

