12.2.2. Definitions of Severity

AEs will be graded using the Common Terminology Criteria for Adverse Events (CTCAE) v.4.0.

Note that “seriousness” and “severity” are distinct concepts. “Serious” is a term applied to an AE that meets specific requirements (refer to Section [12.2.1](#)). “Severity” refers to the AE intensity classification.

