13.2.10.4. Clinical Laboratory Results

Summary statistics for actual values and for change from baseline will be tabulated as appropriate for laboratory results by scheduled visit, disease and cohort. Subjects with laboratory

values outside of the normal reference range at any post-baseline safety assessment will be listed by visit, disease and cohort.

Shifts from baseline laboratory values (normal/abnormal) will be tabulated by disease and cohort.

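### The normal/abnormal laboratory shift table records no shift when a subject who enters abnormal worsens severely, and no planned table of laboratory results counts worsening by severity and treatment

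*SAP*

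**What the plan says.** SAP 13.5 plans three displays for routine laboratory data: summary statistics of actual values and change from baseline by visit, a listing of subjects with any out-of-range post-baseline value, and a shift table: "Shifts from baseline laboratory values (normal/abnormal) will be tabulated by disease group, cohort and treatment". Protocol 13.2.10.4 has the same two categories: "Shifts from baseline laboratory values (normal/abnormal) will be tabulated by disease and cohort". Neither section mentions a severity grade or a low/high direction, and neither says which post-baseline value enters the shift.

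Protocol 8.1 requires subjects to "Have an eGFR ≥ 30 mL/min/1.73 m² calculated by the MDRD equation" and sets no limit on creatinine itself. The exclusions in Protocol 8.2 include "Have a hemoglobin < 9.0 g/dL", "Have an absolute neutrophil count < 500 cells/mm³" and "Have an ALT or AST > 3.0 x the upper limit of normal". The synopsis gives a different liver-enzyme limit, "aspartate transaminase (AST) > 5.0 x the upper limit of normal". That conflict has to be reconciled, but either limit admits values above normal.

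CTCAE is specified for adverse events (Protocol 12.2.2): "AEs will be graded using the Common Terminology Criteria for Adverse Events (CTCAE) v.4.0". Clinical laboratory tests are a named part of the primary endpoint (Protocol 7.3.1, SAP 6).

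**The concern.** A shift table should show how many subjects moved from their own starting point, and in which arm. With two categories, a subject already outside the range has nowhere worse to go. In a kidney-disease population, some of whom may be on immunosuppressants, that can affect the tests of most interest: creatinine, blood counts and liver enzymes.

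One subject matters here. Cohorts 2 and 3 are randomized 1:1 with about 10 and 18 subjects, so about 5 and 9 per arm. One severe case is 1/5 = 20% or 1/9 = 11% of an arm.

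**Working it through.** The plan states no figure to reproduce. The check is which values the entry criteria admit, how the stated rule classifies them, and what the other displays show.

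**1. Creatinine admitted by the eGFR limit.** Protocol 19.1 gives eGFR = 175 × SCr^(−1.154) × age^(−0.203), × 0.742 if female (race factor taken as 1). Solving for creatinine:

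SCr = [eGFR ÷ (175 × age^(−0.203) × 0.742 if female)]^(−1/1.154)

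For a man aged 40, 175 × 40^(−0.203) = 82.8, and (30/82.8)^(−1/1.154) = 2.41 mg/dL. In the same way (mg/dL):

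| | eGFR 30, age 18 | eGFR 30, age 40 | eGFR 30, age 65 | eGFR 60, age 40 |
|---|---|---|---|---|
| Men | 2.77 | 2.41 | 2.21 | 1.32 |
| Women | 2.14 | 1.86 | 1.71 | 1.02 |

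The documents give no reference ranges. With an assumed upper limit of 1.1 to 1.4 mg/dL, everyone at the eGFR 30 limit starts abnormal. At eGFR 60 and age 40, a woman (1.02) starts normal, and a man (1.32) starts abnormal at an assumed limit of 1.3 but normal at 1.4.

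**2. Classification of illustrative changes in admissible subjects.**

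| Test | Baseline → later | Assumed limit of normal | Result |
|---|---|---|---|
| Creatinine, mg/dL | 1.6 → 3.2 | upper, 1.1 to 1.4 | abnormal → abnormal |
| Creatinine, mg/dL | 2.0 → 6.0 | upper, 1.1 to 1.4 | abnormal → abnormal |
| Hemoglobin, g/dL | 9.5 → 6.5 | lower, 11.5 to 13.5 | abnormal → abnormal |
| Neutrophils, per mm³ | 900 → 200 | lower, 1500 to 2000 | abnormal → abnormal |
| ALT, × ULN | 2.9 → 20 | none needed | abnormal → abnormal |

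For a man aged 40, the first row is eGFR 82.8 × 1.6^(−1.154) = 48.1 falling to 82.8 × 3.2^(−1.154) = 21.6. The result is the same across each assumed range. An ALT of 4.9 × ULN at entry, admissible only under the synopsis limit, gives the same answer.

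**3. What the other planned displays show.**

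- *By-visit summaries.* Protocol 13.2.1 includes minimum and maximum, so an extreme change can be seen. But footnote 1 to SAP Table 2 keeps only the assessment closest to the target day in each window. Follow-up Visit 4, for instance, spans days 222 to 312, which is 312 − 222 + 1 = 91 days, and contributes one value. A severe unscheduled result can drop out, and the statistics do not count affected subjects.
- *Out-of-range listing.* It covers any post-baseline assessment. As described, it carries no grade, does not separate new from pre-existing abnormality, and gives no incidence.
- *Creatinine and eGFR (SAP 12.8, 12.9).* These give group mean changes with confidence intervals. They do not count subjects and do not cover blood counts or liver enzymes.
- *Adverse events (SAP 13.1, 13.2).* Treatment-emergent events are tabulated by maximum CTCAE grade. Protocol 12.3.1 counts clinically significant laboratory findings as adverse events, but Protocol 12.1 adds that there must be symptoms or a need for intervention. Under 12.1, an asymptomatic, untreated change need not be reported or graded.

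**The case against.** The strongest reply is that one table is being judged as if it stood alone. The summaries are not means only. A creatinine rise from 1.6 to 3.2 in one of nine subjects, the rest unchanged, moves the mean by just 1.6/9 = 0.18 mg/dL, but it appears in full as a maximum change of 1.6. With about 44 subjects, the listing can be read case by case. Renal function has its own analyses, with between-arm differences for eGFR in Cohorts 2 and 3. Some laboratory worsening will reach the graded adverse-event tables. The study is descriptive, so no estimate is biased and nothing goes unrecorded.

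All of that stands, and it limits the point. A reader might infer that severe worsening would be invisible in the report; the documents do not support that. Nor do they support saying that most subjects start abnormal or that the listing will include nearly everyone: entry criteria set limits, not distributions, and no baseline laboratory data are given. That a move from low to high would also count as no shift follows from the two category names, but table shells are documented separately (SAP 20.1) and might split the abnormal category.

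What the reply does not supply is a count of subjects who worsened, by severity and arm, for blood counts and liver enzymes in particular.

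**Conclusion.** The point holds as a gap in display. Under the stated rule, a subject who enters with an abnormal creatinine, hemoglobin, neutrophil count or ALT/AST and then worsens severely is tabulated as no shift. A subject who enters normal does show a shift, but without severity. The graded adverse-event tables fill the gap only for changes reported as adverse events.

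The number of subjects affected is not derivable. The creatinine, hemoglobin and neutrophil examples rest on assumed reference limits, with ranges shown; the ALT example needs none. This is an inexpensive improvement to how part of the primary endpoint is reported. It is not a loss of data or an error in any estimate.

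**What to change.** In SAP 13.5, replace the normal/abnormal shift with:

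- baseline against worst post-baseline CTCAE v4.0 grade, for tests that have grades, with high and low directions separate and unscheduled values included;
- baseline against post-baseline low/normal/high for the remaining tests;
- for creatinine, also the number of subjects reaching 1.5 and 2 times their own baseline. This does not depend on reference ranges, which may differ because Protocol 12.1.1 allows a central or local laboratory.

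Keep the breakdown by disease group, cohort and treatment.

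The cost is added derivation (CTCAE is now specified for adverse events, not laboratory values), table programming and larger tables. No new samples or visits are needed. Record the change in SAP 21.1 and describe it in the clinical study report. Protocol 13.2 requires an amendment only if a principal feature of the protocol is altered, which this change is unlikely to do.
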